# **CLINICAL TRIAL SUMMARY**

COMPOUND: SAR236553 (Praluent/Alirocumab)	STUDY No: LPS14354 STUDY NAME: ODYSSEY DM-Dyslipidemia					
TITLE	A Randomized, Open-Label, Parallel Group Study to Evaluate the Efficacy and Safety of Alirocumab versus Usual Care in Patients with Type 2 Diabetes and Mixed Dyslipidemia at High Cardiovascular Risk with Non-HDL-C Not Adequately Controlled with Maximally Tolerated Statin Therapy					
INVESTIGATOR/TRIAL LOCATION	Multinational-Multicenter					
PHASE OF DEVELOPMENT	3b/4					
STUDY OBJECTIVE(S)	Primary objective:					
	
 
To demonstrate the superiority of alirocumab in comparison with usual care in the reduction of non-high-density lipoprotein cholesterol (non-HDL-C) after 24 weeks of treatment in patients with Type 2 diabetes and mixed dyslipidemia at high cardiovascular (CV) risk with non-HDL-C not adequately controlled with maximally tolerated statin therapy.
 
					
	Secondary objective(s):					
	
 
To demonstrate whether alirocumab is superior in comparison with usual care in its effects on other lipid parameters at Weeks 12 and 24 (ie, low-density lipoprotein cholesterol (LDL-C), apolipoprotein B (Apo B), total cholesterol (Total -C), lipoprotein a (Lp[a]), high-density lipoprotein cholesterol (HDL-C), triglycerides (TGs), triglyceride rich lipoproteins (TGRLs), apolipoprotein A-1 (Apo A-1), apolipoprotein C-III (Apo C-III), lipid subfractions by nuclear magnetic resonance (NMR) spectroscopy (ie, LDL particle size and LDL, very low-density lipoprotein (VLDL), HDL, intermediate-density lipoprotein (IDL) particle number)
 
					
	
 
To demonstrate the superiority of alirocumab in comparison with usual care in the reduction of non-HDL-C at Week 12.
 
					
	
 
To assess changes in diabetes related parameters in patients randomized to alirocumab vs. usual care treatment over a period of 24 weeks
 
					
	To demonstrate the safety and tolerability of alirocumab					
	
 
To evaluate changes in proprotein convertase subtilisin kexin type 9 (PCSK9) concentrations at Weeks 12 and 24
 
To evaluate the development of anti-alirocumab antibodies
 
To demonstrate the superiority of alirocumab versus fenofibrate therapy on non-HDL-C and other lipid parameters
 
					
STUDY DESIGN	This is a Phase 3b/4 randomized, open-label, parallel group study to assess the efficacy and safety of alirocumab administered by subcutaneous (SC) injection versus usual care in patients with Type 2 diabetes and mixed dyslipidemia at high CV risk with non-HDL-C not adequately controlled with maximally tolerated statin therapy.  Patients will be taking a stable, maximum dose/regimen of statin that is					

tolerated by the patient without other lipid modifying therapies at baseline. Patients may be on no statin if unable to tolerate statin therapy as judged by the investigator.

Randomization will be unbalanced (2:1, alirocumab:usual care). The study will be a multinational, multicenter study.

Usual care includes the option to continue on the maximum dose of statin that is tolerated by the patient without the addition of a new lipid modifying therapy (LMT) at randomization, or the initiation of either ezetimibe, fenofibrate, omega-3 fatty acids, or nicotinic acid at randomization for the remainder of the 24-week treatment period. Initiation of usual care treatment investigational medicinal product (IMP) should start as soon as possible after randomization, but no later than 7 days from the day of randomization.

The Investigator will select the most appropriate LMT for the patient prior to randomization (consisting of either no additional LMT but continuing on maximum tolerated statin, ezetimibe, fenofibrate, omega-3 fatty acids or nicotinic acid) and enter this information into the interactive voice response system (IVRS). If the patient is randomized to open label alirocumab, the Investigator will not institute the LMT option that was selected and entered into IVRS but instead treat the patient with open label alirocumab. If the patient is randomized to usual care (non-alirocumab), the Investigator will initiate treatment with the LMT option that was selected and entered into IVRS, as applicable, in addition to continuing the patient on the maximum tolerated dose of statin.

Randomization will be stratified by the Investigator's selection of usual care therapy prior to randomization (for example, the intent to prescribe fenofibrate, intent to prescribe ezetimibe, etc). This will help ensure balanced treatment groups with patients' characteristics as homogenous as possible. Recruitment of patients will complete when ~420 patients have been randomized.

Patients randomized to open label alirocumab will continue on the maximum dose of statin that is tolerated by the patient and will administer alirocumab SC with a starting dose of 75 mg every 2 weeks (Q2W) for 12 weeks with a blinded uptitration to alirocumab 150 mg Q2W at week 12 if the non-HDL-C at the week 8 visit is ≥100 mg/dL (2.59 mmol/L). Patients who have a non-HDL-C <100 mg/dL (2.59 mmol/L) at the Week 8 visit will continue with alirocumab 75 mg Q2W until the end of the treatment period.

No changes during the course of the study will be made to the dose of LMT administered as part of the usual care arm except for nicotinic acid for which the Investigator may prescribe at randomization a scheduled/gradual dose titration in order to allow for the maximum dose to be achieved based on patient tolerability or except if needed for any usual care LMT for the safety of the patient, based on the Investigator's judgment.

The study consists of:

- A screening period of up to 3 weeks;
- An open-label treatment period (OLTP) of 24 weeks;
- A safety observation period of 8 weeks.

A phone visit will take place at Week 32 in order to document any adverse event(s) that might occur between Weeks 24 to 32.

Patients should have been previously instructed on a cholesterol lowering diet prior to screening. During the study, the Investigator may reinforce diet

recommendations according to local/regional guidelines. Patients should be receiving antihyperglycemic treatment in accordance with local/ regional standards of care. Changes to antihyperglycemics should be limited and made only in circumstances where it is clinically needed.

Statin dose and dose regimen should be stable throughout the entire study duration including for 4 weeks prior to the screening period and from screening to the end of the open label treatment period.

The data on lipid parameters from blood samples will be masked after randomization. No attempts should be made by the Investigator or patient to have the patient's lipid values independently evaluated after randomization until after the Week 24 visit, except for the safety of the patient as per the Investigator's judgment. At the end of the OLTP (Week 24 visit), the Investigator will continue to manage the patient's lipids in accordance with standard practice. Any lipid values after randomization (eg, if done for patient safety) should be redacted in the source documents and not shared with the Sponsor.

Duration of study treatment will be 24 weeks with the last injection of open label alirocumab administered at Week 22. The treatments prescribed in the usual care arm will be administered for 24 weeks. From the Week 24 visit onward, the Investigator will continue to manage the patient's lipids in accordance with standard practice.

Patients will visit the study site at Weeks -3, 0, 8, 12, 20, and 24 with lab work at each visit; in addition a phone visit is scheduled at Weeks 4 and 32. Week 8 is a critical visit because it will be the only scheduled visit where a non-HDL-C value for uptitration will be available.

#### STUDY POPULATION

#### Main selection criteria

#### Inclusion criteria:

I 01. Patients with Type 2 diabetes and mixed dyslipidemia not adequately controlled with a stable, maximum dose/regimen of statin that is tolerated by the patient\* for at least 4 weeks prior to the screening visit (Week -3) without other LMT.

\*Note: The maximum dose/regimen of statin that is tolerated by the patient is the highest registered dose/regimen tolerated by the patient based on the judgment of the Investigator. Patients not able to be on a maximum dose/regimen of statin should be treated with the dose of statin which is considered appropriate for the patient as per the Investigator's judgment or concerns. Some examples of acceptable reasons for a patient taking a lower statin dose include, but are not limited to: adverse effects on higher doses, advanced age, low body mass index (BMI), regional practices, local prescribing information, concomitant medications. Patients may be on alternate day dosing of statin as long as the dose is consistently taken (eg, dose every Monday, Wednesday, Friday, etc). Concomitant treatment with more than 1 statin is not permitted. Patients who have documented statin intolerance, as judged by the Investigator, and who are no longer on statin therapy as a result will also be eligible for the study. The reason(s) for not being on a maximum dose/regimen of statin (including statin intolerance) will need to be documented in the case report form.

- I 02. Patients ≥18 years of age or legal age of majority at screening visit whichever is greater.
- I 03. Documented history of atherosclerotic cardiovascular disease (ASCVD) or at least one additional CV risk factor.

Notes:

Atherosclerotic cardiovascular disease (ASCVD) includes: coronary heart disease (CHD) and CHD risk equivalents (PAD, ischemic stroke)

History of CHD includes at least one of the following:

- acute myocardial infarction (MI),
- silent MI,
- · unstable angina,
- coronary revascularization procedure (eg, percutaneous coronary intervention [PCI] or coronary artery bypass graft surgery [CABG])
- clinically significant CHD diagnosed by invasive or noninvasive testing (such as coronary angiography, stress test using treadmill, stress echocardiography, or nuclear imaging).

CHD risk equivalents include at least one of the following:

- Documented peripheral arterial disease (PAD) (one of the following criteria [a, b, or c] must be satisfied):
  - a) Current intermittent claudication (muscle discomfort in the lower limb that is both reproducible and produced by exercise and relieved by rest within 10 minutes) of presumed atherosclerotic origin TOGETHER WITH ankle-brachial index ≤0.90 in either leg at rest, OR
  - History of intermittent claudication (muscle discomfort in the lower limb that is both reproducible and produced by exercise and relieved by rest within 10 minutes) TOGETHER WITH endovascular procedure or surgical intervention in one or both legs because of atherosclerotic disease OR
  - History of critical limb ischemia TOGETHER WITH thrombolysis, endovascular procedure or surgical intervention in one or both legs because of atherosclerotic disease.
- Documented previous ischemic stroke with a focal ischemic neurological deficit that persisted more than 24 hours, considered as being of atherothrombotic origin. Computed tomography or magnetic resonance imaging must have been performed to rule out hemorrhage and non-ischemic neurological disease.

Cardiovascular risk factors include at least one of the following:

- hypertension (established on antihypertensive medicine)
- current cigarette smoker
- age ≥45 years for men and ≥55 years for women
- history of micro/macroalbuminuria
- history of diabetic retinopathy (preproliferative or proliferative)
- family history of premature CHD (in father or brother before
   55 years of age; in mother or sister before 65 years of age)
- low HDL-C (male <40 mg/dL [1.0 mmol/L] and female <50 mg/dL [1.3 mmol/L])

- documented chronic kidney disease (CKD) as defined by 15 ≤estimated glomerular filtration rate (eGFR) <60 mL/min/1.73 m^2 for 3 months or more, including the screening visit).
- I 04. Non-HDL-C at screening ≥100 mg/dL (2.59 mmol/L).
- I 05. Triglycerides at the screening visit ≥150 mg/dL (1.70 mmol/L) and

	(FOO (     (F OF         )
	<500 mg/dL (5.65 mmol/L).
	I 06. Stable anti-hyperglycemic agents for at least 3 months prior to the screening visit and between screening and randomization (including stable insulin dose defined as no variation more than 30% in daily insulin dose within the preceding 3 months, as judged by the Investigator).
	I 07. No variation of weight more than 5 kg within 3 months prior to the screening visit or between screening and randomization, as judged by the Investigator.
	I 08. On stable dose of medications that are known to influence weight and/or lipids (other than LMTs) within 3 months prior to the screening visit or during the screening period (eg, estrogen replacement, oral steroids, antipsychotics known to impact weight).
	I 09. Signed written informed consent.
	Exclusion criteria:
	
 
Use of any LMTs other than statins within 4 weeks prior to the screening visit or during the screening period (eg, ezetimibe, fenofibrate, nicotinic acid, omega-3 fatty acids, etc) or use of over the counter products/nutraceuticals known to impact lipids (eg, red yeast rice) within 4 weeks prior to the screening visit or during the screening period.
 

	
 
Currently drinking more than 2 standard alcoholic drinks/day (Note: A standard drink is considered as 1 pint/bottle of beer, 1 glass of wine, or 1 shot of hard liquor).
 

	
 
Body Mass Index (BMI) >45 kg/m^2 at screening or currently enrolled in a weight loss program and still in active phase of weight loss, as judged by Investigator.
 

	
 
HbA1c at screening ≥9%
 

Total expected number of patients	A total of ~420 patients are expected (~280 patients will be randomized to alirocumab and ~140 randomized to usual care).
STUDY TREATMENT(s)	
Investigational medicinal product(s)	Alirocumab (open label).
Formulation:	Prefilled pen; Sterile alirocumab drug product supplied at a concentration of 75 mg/mL or 150 mg/mL in histidine, pH 6.0, polysorbate 20, and sucrose.
Route(s) of administration:	Subcutaneous (SC); 1 injection of 1 mL SC in the abdomen, thigh, or outer area of upper arm (ie, deltoid region)
Dose regimen:	Alirocumab 75 mg Q2W with possible uptitration at Week 12 to 150 mg Q2W. The last planned injection of alirocumab IMP is to be administered at Week 22.
	Note: A placebo injection for training purposes will be administered to the patient at screening, with the option of a second training injection prior to randomization. If the person who is designated to administer alirocumab to the patient changes during the course of the study, the new designated person will be trained with a placebo.
Investigational medicinal	Usual Care (open label).
product(s)	There are five options available in the usual care arm including the option to

	add no additional LMT on top of the maximum dose/regimen of statin that is tolerated by the patient or to start one of the following treatments: ezetimibe, fenofibrate, omega-3 fatty acids or nicotinic acid. All patients, regardless of the usual care option that has been selected, should continue on the maximum dose/regimen of statin (non-IMP) that is tolerated by the patient.
	The following drugs are identified as IMP:
Formulation:	Ezetimibe, or
	Nicotinic acid, or
	Fenofibrate, or
	Omega-3 fatty acids
Route(s) of administration:	Oral
Dose regimen:	As applicable and in accordance with Investigator prescription/local labeling.
Noninvestigational medicinal product(s) (if applicable)  Formulation:	No non-investigational products will be provided by the Sponsor. The following non-investigational products may be taken by the patient, as applicable, and in accordance with the eligibility criteria: statins (HMG CoA reductase inhibitors).
Route(s) of administration:	As applicable and in accordance with local labeling.
Dose regimen:	As applicable and in accordance with local labeling.
ENDPOINT(S)	Primary endpoint:
	
 
Percent change in non-HDL-C from baseline to Week 24 in the intent-to-treat (ITT) population, using all non-HDL-C values regardless of adherence to treatment (ITT estimand).
 

	Key Secondary Efficacy endpoints (ITT estimand)
	Percent change in measured LDL-C from baseline to Week 24.
	Percent change in non-HDL-C from baseline to Week 12.
	Percent change in measured LDL-C from baseline to Week 12.
	Percent change in Apo B from baseline to Week 24.
	Percent change in Total-C from baseline to Week 24.
	Percent change in Lp(a) from baseline to Week 24.
	Percent change in TGs from baseline to Week 24.
	Percent change in HDL-C from baseline to Week 24.
	
 
Percent change in LDL particle number from baseline to Week 24.
 
Diabetes-related endpoints (ITT estimand)
 

	
 
Absolute change in HbA1c from baseline to Weeks 12 and 24.
 
Absolute change in fasting plasma glucose (FPG) from baseline to
 

	

Weeks 12 and 24.

Absolute change in number of glucose-lowering treatments from

	baseline to Weeks 12 and 24.
	Safety endpoints
	
 
Treatment emergent adverse events (TEAEs), adverse events of special interest (AESIs), product complaints, laboratory data
 

(including microalbuminuria), vital signs (including change in body weight and BMI).

#### Other endpoints

- Anti-alirocumab antibodies assessed throughout the study.
- Serum PCSK9 levels assessed throughout the study.

#### Other Efficacy Endpoints (ITT estimand)

- Percent change in calculated LDL-C from baseline to Weeks 12 and 24.
- Percent change in Apo B, Total-C, Lp(a), TGs, and HDL-C from baseline to Week 12.
- Proportion of patients reaching measured LDL-C <50 mg/dL (1.30 mmol/L), <70 mg/dL (1.81 mmol/L) and < 100 mg/dL (2.59 mmol/L) at Weeks 12 and 24.
- Percent change in measured LDL-C according to baseline TGs of <median TG or ≥median TG at Weeks 12 and 24.

- Proportion of patients reaching non-HDL-C <130 mg/dL (3.37 mmol/L), <100 mg/dL (2.59 mmol/L) and <80 mg/dL (2.07 mmol/L) at Weeks 12 and 24.
- Percent change in TGs from baseline to Weeks 12 and 24 according to baseline TGs of <median TG or ≥median TG.

- Percent change in LDL particle number from baseline to Week 12.
- Percent change in LDL particle size from baseline to Weeks 12 and 24.
- Percent change in VLDL, HDL and intermediate-density lipoprotein (IDL) particle number from baseline to Weeks 12 and 24.
- Percent change in Apo A-1 and Apo-C-III from baseline to Weeks 12 and 24.
- Absolute change in TGRLs (ie, non-HDL-C minus LDL-C) from baseline to Weeks 12 and 24.
- Proportion of patients with 50% or greater reduction from baseline in measured LDL-C at Weeks 12 and 24.
- The proportion of patients reaching Apo B <80 mg/dL at Weeks 12 and 24.
- Absolute change in ratio Apo B/Apo A-1, Total-C/HDL-C and LDL-C/HDL-C from baseline to Weeks 12 and 24

#### **ASSESSMENT SCHEDULE**

**V1**: (Week -3, [Day -21 to -8]): screening, alirocumab (placebo IMP) injection training\*, safety.

**V2**: (Week 0 [Day 1 + 3]): baseline, randomization, first administration with open label alirocumab (if the patient is randomized to alirocumab) or initiation of usual care (if the patient is randomized to the usual care (non-alirocumab) arm), and as per the prescription of the Investigator), safety. Patients will have the option to self-inject/inject a second time with placebo after the first screening injection training and before randomization. For patients randomized to alirocumab, additional training can be performed with open

label alirocumab at this visit.

V3: (Week 4[Day 29 ±7 days]): telephone contact.

V4: (Week 8 [Day 57 ±3 days]); V6: (Week 20 [Day 141 ±7 days]): Efficacy and safety assessment parameters.

**V5**: (Week 12 [Day 85  $\pm$ 3 days]): Second allocation of open label alirocumab if randomized to alirocumab or prescription for usual care treatment (IMP) if randomized to usual care (as applicable), efficacy, and safety assessment parameters.

**V7**: (Week 24 [Day 169  $\pm$ 3 days]): End of open label treatment visit, efficacy, and safety assessment parameters.

**V8**: (Week 32 [Day 225 ±7 days]): telephone contact, safety assessment.

\*In case a designated person plans to inject the patient but is not present at the time of the screening visit, a dedicated training visit may be scheduled during the screening period prior to the randomization visit or training can be performed at the randomization visit prior to study drug administration.

Note: If one visit is changed, the next visit should take place according to the original schedule.

Patients who prematurely discontinue treatment should be followed as scheduled.

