## 6.2 DURATION OF STUDY PARTICIPATION

#### 6.2.1 Duration of study participation for each patient

The duration of the study is approximately 9 months to include:

Property of the Sanofi Group - strictly confidential

- a 3-week screening period from signed informed consent form (ICF) to randomization
- a 24-week OLTP
- a safety observation period of 8 weeks after the end of the OLTP

Note, the Investigator will need to document in the CRF any AEs that have occurred up to Study Day 225. A phone visit will take place at Week 32 in order to ensure documentation of any AEs that might occur during this period. If the patient prematurely discontinues the study:

- if treated with IMP, AEs would need to be reported up to 70 days after the last dose of IMP or Study Day 225, whichever comes first (even if patient continues on the usual care treatment that was added at randomization after discontinuing the study).
- if randomized to usual care without additional LMT, AEs would need to be reported up to 70 days after the last on-site study visit, or Study Day 225, whichever comes first.

Patients with an SAE or an adverse event of special interest (AESI) should be followed until resolution, stabilization, or death.

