## 8.1.1.2 Timing of administration

During the screening period, patients or the designated person will have to perform a placebo self-injection training using a prefilled pen, before randomization and the first alirocumab injection.

At the randomization visit, the first alirocumab injection will be done at the site by the patient or another designated person (such as spouse, relative, etc) under direct site staff supervision. Patients will be monitored at the investigational site for at least 30 minutes after this first injection in this study. If the designated person changes during the course of the study, the new designated person will need to be trained with placebo prior to administering alirocumab to the patient.

Alirocumab SC injections will then be performed outside of the clinic, Q2W up to the last injection. If the injection is scheduled to take place on the same date as the site visit, then alirocumab should be administered after the blood sampling has been completed. In exceptional cases, if a patient prefers to have the injection performed at the study site and provisions are able to be made to accommodate the administration of injections at the site, it may also be allowed.

18-Nov-2015 Version number: 1

Alirocumab should be administered SC Q2W, ideally at approximately the same time of the day; however, it is acceptable to have a window period of  $\pm 3$  days. The time of the day is based upon the patient's preference.

If by mistake or due to other circumstances an injection is delayed by:

- more than 7 days from the missed date or completely missed, then the patient should return to the original schedule of alirocumab administration without administering delayed injections.
- less than or equal to 7 days from the missed date, then the patient should administer the delayed injection and then resume the original schedule of alirocumab administration.

Please note that injections should not be administered within less than 7 calendar days. Please refer to Section 10.4.1.3 for the definition of overdose with alirocumab.

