#### 9.2.3.1 Adverse events

Refer to Section 10.4 to Section 10.6 for details.

All AEs diagnosed by the Investigator will be reported and described.

All AEs will be coded to a "Lowest Level Term (LLT)", "Preferred Term (PT)", "High Level term (HLT)", "High Level Group Term (HLGT)" and associated primary "System Organ Class (SOC)" using the version of MedDRA (Medical Dictionary for Regulatory Activities) currently in effect at Sanofi at the time of the considered database lock.

Adverse events/AESIs, SAEs, and product complaints will be collected from the time the patient signs the ICF to the last scheduled study visit.

Definitions for AEs, SAEs, and AESI, as well as obligation for reporting are further defined in Section 10.4.1 and Section 10.5.

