## 10 STUDY PROCEDURES

The window period for Week 0 is  $\pm$  3 days. The window period for Weeks 8, 12 and 24 is  $\pm$ 3 days. The window period for Weeks 4, 20, and 32 is  $\pm$ 7 days.

For all visits after Day 1/inclusion visit, if one visit date is changed, then the next visit should take place according to the original schedule as outlined in the Study Flow Chart Section 1.2.

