# Observation period

The observation period will be divided into 3 periods:

- Pre-treatment period is defined from the signed informed consent up to the day before the first dose of open-label alirocumab injection/first dose of usual care treatment for those prescribed another LMT if allocated to the usual care arm. For those allocated to the usual care arm for whom another LMT is not prescribed, the pre-treatment period will end on the day before randomization.
- Treatment Emergent Adverse Event (TEAE) period:
  - o For patients randomized to alirocumab, the TEAE period is defined as the time from the day of the first dose of open-label alirocumab injection to the day of the last dose of open-label alirocumab injection + 70 days (10 weeks) as residual effect of treatment is expected until 10 weeks after the stop of alirocumab.
  - For patients randomized to usual care
    - and who are administered an additional LMT, the TEAE period is defined as the time from the day of the first intake of the usual care drug to 70 days after the day of the last intake or Study Day 225, whichever comes first.
    - and for whom the Investigator has not prescribed an additional LMT, the TEAE period is defined as the time from the day of randomization to the date of the last on-site visit + 70 days, or Study Day 225, whichever comes first.
- Post-treatment period is defined as the time starting the day after the end of the TEAE
  period up to resolution/stabilization of all serious adverse events (SAEs) and AEs of
  special interest (AESI), whichever comes last.

The on-study observation period is defined as the time from the day of the first dose of open-label alirocumab injection/first dose of usual care treatment (for those prescribed another LMT if

allocated to the usual care arm)/randomization (for those allocated to the usual care arm for whom another LMT is not prescribed) until the last protocol planned visit of the patient (Week 32 phone call).

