Reasons for treatment discontinuation will be supplied in tables giving numbers and percentages by treatment group. A listing of patients who prematurely discontinued study treatment with further reason provided in free text will be provided.

The incidence of premature treatment discontinuation (irrespective of the reason) and premature treatment discontinuation due to AEs will be presented graphically by treatment group on randomized and treated patients (as treated), using Kaplan-Meier method.

The incidence of premature study discontinuation (irrespective of the reason) and premature study discontinuation due to AEs will be presented graphically by treatment group on randomized and treated patients (as treated), using Kaplan-Meier method.

Patients with insufficient post-treatment follow-up will be described on the safety population by treatment group. Number and percentage of patients with insufficient follow-up, quantitative (in weeks) and qualitative ( $<1, \ge 1$  to  $<3, \ge 3$  to  $<5, \ge 5$  to  $<7, \ge 7$  to <9 weeks) duration of follow-up will be presented by treatment arm. A patient is considered with insufficient post-treatment follow-up in the case of his/her last post-treatment phone-call is:

- For patients receiving alirocumab: less than 9 weeks after the last open-label alirocumab injection, unless patient died before
- For patients receiving another LMT in the usual care arm:
  - o less than 9 weeks after the last dose of usual care treatment or
  - o before Week 31,

26-Apr-2017

whichever comes first, unless patient died before

- For patients randomized to usual care without LMT:
  - o less than 9 weeks after the last on site study visit or
  - before Week 31,
     whichever comes first, unless patient died before.

All major deviations potentially impacting efficacy analyses, randomization, and drug-dispensing irregularities, and other major or critical deviations will be summarized in tables giving numbers and percentages of deviations by treatment group. Patients excluded from the ITT population will be listed as well as patients with major deviation potentially impacting efficacy analyses not resulting in exclusion from ITT population. These deviations are listed in the data review and surveillance plan.

Additionally, the following analysis populations will be summarized by treatment group:

- Randomized population;
- Efficacy population: ITT population;
- Safety population;
- PCSK9 population;
- ADA population.

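### The Week 32 safety call may be made up to a week before the adverse-event period it should close, yet event-free patients are counted to the end of that period

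*Protocol*

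**What the plan says.** **Timing of the call.** The assessment schedule in the protocol synopsis lists "Week 32 [Day 225 ±7 days]): telephone contact, safety assessment". The flow chart (Section 1.2) has the same two-sided window, and Section 10 repeats it: "The window period for Weeks 4, 20, and 32 is" ±7 days. No other contact is scheduled after the Week 24 visit.

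**Purpose of the call.** Protocol 6.2.1 states: "Note, the Investigator will need to document in the CRF any AEs that have occurred up to Study Day 225". It then adds: "A phone visit will take place at Week 32 in order to ensure documentation of any AEs that might occur during this period". The heading of Section 10.1.2.5 equates Week 32 with 10 weeks after the last alirocumab injection.

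**End of AE collection.** Protocol 9.2.3.1 uses a visit instead of a study day: "Adverse events/AESIs, SAEs, and product complaints will be collected from the time the patient signs the ICF to the last scheduled study visit". SAP 2.1.4 likewise ends the on-study period at the Week 32 call.

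**TEAE period.** For alirocumab, SAP 2.1.4 runs it to the last injection plus 70 days, "as residual effect of treatment is expected until 10 weeks after the stop of alirocumab", with no cap at Day 225. For usual care it ends at Day 225 at the latest.

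**Late injections.** Under protocol 8.1.1.2, if the delay is "less than or equal to 7 days from the missed date, then the patient should administer the delayed injection". The routine injection window is ±3 days.

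**Short follow-up.** SAP 2.2 calls follow-up insufficient if the last call is: "For patients receiving alirocumab: less than 9 weeks after the last open-label alirocumab injection, unless patient died before". This is reported descriptively.

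**Analysis.** In SAP 2.4.5.1, event-free patients are censored at the end of the TEAE period in Kaplan-Meier analyses and contribute its full length to patient-years. Protocol 11.4.3.1 has the same censoring rule.

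**The concern.** A call meant to secure AE documentation to Day 225 cannot do so if it is made on Day 218, yet that date is within the window. The call is timed from randomization, whereas the alirocumab TEAE period is timed from the last injection, so a late last injection widens the gap.

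The analysis does not adjust for this. A patient last contacted on Day 218 with no event reported is treated as event-free to the end of the TEAE period. Events in the uncovered days can be missed from the numerator while the days stay in the denominator. The possible gap is larger on alirocumab, because only usual care is capped at Day 225.

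**Working it through.** **Inputs.** Study day = 1 + 7 × week. The last injection is at Week 22 (protocol 6.1), the call window is Day 225 ±7, and a dose up to 7 days late is still given.

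**The plan's own figure.** Week 22 is 1 + 154 = Day 155, and 155 + 70 = 225. Week 32 is 1 + 224 = Day 225. The two definitions agree exactly for an on-time last injection.

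**Earliest call.** 225 − 7 = Day 218.

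**Gap** = max(0, TEAE end − call day). TEAE end is last injection + 70 for alirocumab. For usual care it is the earlier of Day 225 and 70 days after the last intake (or after the last on-site visit if no therapy was added).

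| Case | TEAE end | Gap, call Day 218 | Gap, call Day 225 | Last dose to Day 218 | Flagged at Day 218? |
|---|---|---|---|---|---|
| Alirocumab, 3 days early (Day 152) | 222 | 4 | 0 | 66 days | No |
| Alirocumab, on time (Day 155) | 225 | 7 | 0 | 63 days | No |
| Alirocumab, 3 days late (Day 158) | 228 | 10 | 3 | 60 days | Yes |
| Alirocumab, 7 days late (Day 162) | 232 | 14 | 7 | 56 days | Yes |
| Usual care, treated or seen to Week 24 | 225 | 7 | 0 | – | see below |

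A call on Day 232 leaves no gap in any row.

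**The flag.** Nine weeks is 63 days. The on-time case gives 218 − 155 = 63, which is not less than 63, so it is not flagged. A Day 225 call after a Day 162 injection also gives 63 and is also not flagged. The alirocumab threshold therefore tolerates any gap of up to 7 days. For usual care, SAP 2.2 adds a limit of before Week 31, whichever comes first. Week 31 is Day 218, so on the natural reading a Day 218 call is not flagged there either.

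**Share of the TEAE period.** 7/225 = 3.1% and 14/232 = 6.0%. Relative to the 218 days covered, person-time in such patients is overstated by 7/218 = 3.2% or 14/218 = 6.4%.

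**Illustration of missed events.** Assume a constant hazard h = −ln(1 − r)/225, where r is the cumulative incidence by Day 225, and no spontaneous reporting. The missed incidence is exp(−218h) − exp(−225h) for the 7-day gap and exp(−218h) − exp(−232h) for the 14-day gap. The values of r are assumptions.

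| r | 7-day gap | 14-day gap |
|---|---|---|
| 10% | 0.3 points | 0.6 points |
| 30% | 0.8 points | 1.6 points |
| 60% | 1.2 points | 2.3 points |

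These figures apply only to patients called on Day 218. The documents give no basis for how many that would be.

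**The case against.** **The nominal design is right.** The target day equals the last injection plus 70 days, and ±7 days is an ordinary visit tolerance. This stands. A reader might infer that the trial fails to deliver 10 weeks of follow-up in general. It does not: an on-time injection with a call on or after Day 225 delivers it in full.

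**The days are not wholly unobserved.** A reader might infer that AEs in the gap cannot be recorded. At Week 24 patients are reminded to report AEs up to Day 225 (protocol 10.1.2.4), and the investigator must document AEs to Day 225 whenever the call is made. An SAE learned of after study end and judged caused by alirocumab is still reportable (10.4.3). What is missing is scheduled contact, which matters most for minor late events.

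**Fourteen days is a worst case.** It needs the longest permitted delay and the earliest permitted call together, on alirocumab only, and SAP 2.2 flags it. This stands, but the flag leaves censoring and person-time unchanged.

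**The 9-week threshold follows from the visit window.** It is 10 weeks less the tolerance. That explains it, but the flag then cannot detect the shortfall that the tolerance creates. Protocol 10.3.4 asks for at least 10 weeks from the last dose in patients who stop treatment and decline the remaining schedule.

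**The shares are small.** Seven and 14 days are 10% and 20% of the 70-day tail, and a reader might take those as the bias. The affected rates use the whole TEAE period, where the shares are about 3% and 6%. Safety analyses are descriptive, and crude n (%) tables contain no person-time, although they too can miss late events.

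**Conclusion.** The point holds as a mismatch of modest size. With an on-time last injection, or in usual care treated or seen to Week 24, a compliant call can leave up to 7 days of the TEAE period (about 3%) without scheduled contact; on alirocumab the SAP does not flag this. Only on alirocumab, with a last injection 7 days late and the earliest call, does the gap reach 14 days (about 6%), and that case is flagged. Because event-free patients are counted to the end of the TEAE period, patient-year and Kaplan-Meier rates are biased slightly downward where calls are early and events in the gap go unreported.

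The size rests on the call being made on Day 218, and it shrinks with each later day. The documents do not support a claim that the safety conclusions are invalid. They do need reconciling: protocol 6.2.1 ends AE collection at Day 225, protocol 9.2.3.1 at the last scheduled visit, and SAP 2.1.4 lets the alirocumab TEAE period run past both.

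**What to change.** 1. **Call window** (synopsis, Sections 1.2 and 10). Make it one-sided: not before Day 225 and, on alirocumab, not before 70 days after the last injection, with +7 days counted from the later of the two. Every gap in the table then becomes 0. Day 225 alone would still leave 3 or 7 days after a late injection. A fixed upper limit of Day 232 would leave a single permissible day after a Day 162 injection.
2. **End of AE collection.** Reconcile protocol 6.2.1 and 9.2.3.1 with SAP 2.1.4, so that collection covers the whole TEAE period in each arm.
3. **SAP 2.4.5.1.** End patient-years and Kaplan-Meier follow-up of event-free patients at the earlier of last contact and the end of the TEAE period, and align protocol 11.4.3.1. SAP 2.4.5.3 already censors laboratory abnormalities at the last assessment. This step also covers patients lost or called early despite step 1.
4. **SAP 2.2.** Set the alirocumab threshold at less than 10 weeks, and review the usual-care limits, which carry the same tolerance.

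**Cost.** An amendment to the window wording and a few SAP lines, with no added visit or procedure. Some calls move a week or so later. After a Day 162 injection the window would be Day 232 to Day 239, a week beyond the present limit. Slightly more patients may be reported with insufficient follow-up.
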